3.3.3 Exploratory Endpoints

Changes in self-reported weight, mediators of behavior change, and patient-reported psychosocial/quality of life outcomes.

3.4 Study Approach

Behavioral Framework. Intervention educational and motivational content for the study will be based on Social Cognitive Theory (SCT) and Self Determination Theory (SDT), which targets specific behavioral constructs (i.e., knowledge, self-efficacy, barriers and motivators).¹⁴ These behavioral theories provide a comprehensive framework to identify behavioral strategies to increase patients' intrinsic motivation, confidence in their abilities, and expectations about improvements in their health.⁸⁻¹¹ This combined framework can provide relevant targets to build supportive environments to foster motivation, confidence, and outcome expectations in nutrition and PA behavioral interventions for Latino adults.^{10,11}

SCT explains confidence in one's capability to change a behavior (i.e., self-efficacy) and expectations around engaging in a behavior.¹² A limitation of using SCT alone is that it does not fully address two key constructs: intrinsic motivation and the environment, which are important for initiating and sustaining behaviors.^{10,11} Self-Determination Theory (SDT) incorporates these two constructs into a broad motivational theory to explain why and how individuals behave.^{10,11} Intrinsic motivation is a desire to engage in an activity to achieve an internal sense of reward, satisfaction, or enjoyment. Individuals feel intrinsically motivated by being able to engage in challenging, achievable activities (i.e., competence) and being able to make their own choices about their behaviors (i.e., autonomy). To achieve this internal sense of satisfaction, improve confidence and achieve expectations, an autonomy-supportive environment provided by educators or eHealth communication can help an individual make better dietary and PA choices to improve health and reach their goals.

Behavioral Targets. All participants will be advised on nutrition and PA goals: 1) progressively adhering to high-quality diets by increasing intakes of fruits, vegetables and whole grains; and decreasing intake of energy-dense, nutrient-poor foods (i.e., processed foods, refined grains and added sugars), and 2) progressively reaching an optimal target of ≥ 150 minutes per week of MVPA.

Setting. The study will take place in the Lower Valley of Washington State's Yakima County. Yakima is the second largest county in the state by size and largely agricultural.¹³ The Lower Valley region of the county includes the highest concentration of Latinos (69%) in Washington state, the majority of which are 1st and 2nd generation Mexican-Americans.¹⁴ The region is characterized by high poverty levels, with 21% of the

population living below the poverty line, compared to 13% nationally.¹⁵ The Community Need Index (CNI), which identifies the severity of health disparities for every U.S. zip code, ranks the LYV's zip codes from 4.2 to 5.0 where 5.0 is the highest level of severity of health disparities.¹⁶ Our previous research shows up to 70% of adult Latinos in the Lower Valley have less than an 8th grade education.^{17,18}

Community Health Educators (CHEs). Our CHEs (*promotores*) are male and female Latino bilingual and bi-cultural community members, trained to deliver health education, in qualitative and quantitative research methods, and have worked in the target community for 5-15 years.¹⁹⁻²² For the purpose of this study, key functions of the CHEs include: participant recruitment, assisting during intervention activities, documenting implementation process, and/or coordinating and supporting data collection. As members of the community they serve, the CHEs are familiar and connected with their community thereby enhancing cultural competency of the research methods and the participants' level of comfort and trust with intervention delivery. They also serve as community stakeholders empowered to advocate for community health interests. All CHEs are required to complete and maintain human subjects, information privacy, and confidentiality certification.

Consultant. One community collaborator (trained local Chef) will participate in the delivery of the intervention. The collaborator has undergone 16 hours of training to ensure accurate delivery of the intervention content in the given timeframe. The training included human subjects' certification, orientation to the intervention content, and mock intervention delivery session prior to actual intervention delivery. He is known in the community through the creation of online recipe videos, and has the equipment and expertise needed to deliver nutrition content remotely.

3.5 Estimated Accrual

Based on previous studies with Latino cancer survivors in Yakima Valley, we expect target enrollment of up to 25 participants. The 25 participants will be recruited using methods successfully utilized by [name] to recruit Latino adults who meet the study eligibility criteria in the Lower Yakima Valley: 1) print and radio advertisements by bilingual/bicultural research staff at local retailers, community events, churches, and medical facilities, 2) through social media, and 3) mailing flyers to participants of previous studies that provided prior consent to contact.¹⁰ For individuals who provided prior consent to contact, if there is no response from the potential participant within 1-week of mailing, the CHE will follow-up with 1 phone call to determine interest. CHEs will screen all interested participants via telephone. The eligibility screener is provided in [Appendix A](#).

3.6 Name of Sponsor/Funding Source: CCSG Pilot Funds

4.0 SUBJECT ELIGIBILITY

4.1 Inclusion Criteria

4.1.1 Demographic Data

- Participants must self-identify as being at least 18 years of age or older.
- Participants must self-identify as Latino.
- Participants must be a resident of the Lower Yakima Valley (LYV) and anticipate remaining in the LYV for at least 1 year.
- Participants must speak Spanish or English and fully understand Spanish for online group sessions.

4.1.2 Disease Related Criteria

Participants must meet one of the following disease-related criteria:

Hypertension

- Participants must self-identify as having a medical history of hypertension

Diabetes

- Participants must self-identify as having a medical history of diabetes

Cardiovascular Disease

- Participants must self-identify as having a medical history of cardiovascular disease

Obesity

- Participants must self-identify as having a medical history of obesity, as defined by a BMI of $>30 \text{ kg/m}^2$

Cancer

- Participants must self-identify as having a medical history of cancer (excluding non-melanoma skin cancer). All other cancer types will be included provided;
- there is no evidence of recurrent or metastatic disease; and
- the patient has not received a bone marrow, stem cell, or cord blood transplant

4.1.3 Prior/Current Therapy Criteria

- For cancer survivors, participants must self-identify as being at least 60 days post final chemotherapy, biologic therapy, or radiation therapy treatment and/or surgery. Current use of hormonal therapy is permitted (e.g., tamoxifen and aromatase inhibitors).

4.1.4 Accessibility Criteria

- Participants must be willing and able to receive text messages via cellphone for 3-6 months.
- Participants must be willing and able to attend six 120-minute online group sessions.
- Participants must be willing to complete the surveys, and diet/PA assessments.

4.1.5 Clinical/Laboratory Criteria

- Participants must not be active smokers within the past 30 days. Active smoking is defined as any smoking, even a puff. Participants who smoke are much less likely to engage in healthy lifestyle behaviors, and it is probably more important for participants to stop smoking than it is to change their dietary patterns. If identified as a smoker, the individual will be referred the CDC “Quit Now” phone line which supports smoking cessation, or the NIH quite support website “SmokeFree.gov which are both available in English and Spanish.
- Participants who report having been told by a health professional they have diabetes or cardiovascular disease must provide a clearance from their physician for participation ([See Appendix B for Medical Release Form](#)).
- Participants must consume <5 servings of fruits and vegetables per day and/or engage in <150 minutes per week of moderate to vigorous physical activity, as assessed by brief questionnaires.^{23,24}
- Participants must have an ECOG Scale of Performance Status Score of 0 or 1 for performance status ([Appendix C](#)). These scales and criteria are commonly used by doctors and trained research staff to assess a person’s daily living abilities. Scores of 0 and 1 corresponds to being fully active, able to carry on all pre-

disease performance without restriction; and restricted in physically strenuous activity but ambulatory and able to carry out work of a light or sedentary nature, respectively.

- Women must not be pregnant at time of enrollment.

- **4.1.6 Ability to understand and the willingness to sign an online informed consent document**
- Depending on preference, the consent will be provided in English or Spanish.

5.0 SUBJECT REGISTRATION

Eligible participants will be identified by the Center for Community Health Promotion Study Staff who will register the patient by contacting the Fred Hutch Study Coordinator who will enter their information into the secure REDCap database. A complete, electronically signed, study consent and HIPAA consent are required for registration.

6.0 STUDY PROCEDURES AND INTERVENTION

Figure 1. Study Flow Chart

[figure not shown]

Table 1. Data Collection Overview

MEASURE	Screening	Baseline	Follow-up
		T1	T2
Eligibility criteria	X		
At-home assessments:			
Demographic and clinical characteristics		X	
Self-reported weight		X	X
Dietary Intake and PA measures:			
Social and Behavioral measures:			

Physical Activity Questionnaire		X	X
Psychosocial/Quality of Life Outcomes		X	X
Nutrition and physical activity knowledge and preferences		X	X
Exit Interviews on intervention acceptability			X

6.1 Informed Consent and Baseline Data Collection

Informed Consent. Prior to any baseline data collection, CHEs will orient participants to the study activities, rights and responsibilities and will provide electronic informed consent via a HIPPA-compliant and secured REDCap electronic form (eConsenting) for participation in the intervention program and data collection procedures, including the release of medical records regarding diagnosis and treatment for condition identified for study eligibility. Research staff will review the study in detail and outline participant involvement during the screening process over the phone. Research staff will discuss the consent process with the potential participant prior to providing consent online. All items in the informed consent will be discussed, including why the study is being conducted, the number of people participating, what is involved in the study, how long the participant will be in the study, the risks and benefits of the study, alternatives to participation, confidentiality, rights as a participant, and who to call with questions or concerns. Participants will be encouraged to contact research staff any time they have concerns or questions about the study. Each consent is implemented in REDCap using the survey functionality. The survey functionality presents the pages of the traditional paper consent, including the IRB stamp, to a potential research subject, then uses REDCap to present the questions and signature fields that appear on the paper consent. Once an individual agrees to participate, electronically signs the informed consent, then hits submit, a PDF of the completed consent can be automatically generated and saved to a REDCap form to preserve the exact consent text along with the research subject's responses. Informed consents will be provided in Spanish and English, depending on participant's preference. To make this less burdensome, we will collect their doctor/medical institution information as part of the medical release form and our staff can directly contact their doctors to acquire their clearance, when needed. See Appendix B for the consent and medical release form in English—provided in English for initial IRB approval and will be subsequently translated in Spanish.

Baseline Data Collection. Eligible participants will undergo remote baseline assessments that will include at-home, over the phone and web-based data collection and a “run-in” within an 8-week period prior to the start of the intervention (see [Figure 1](#)). Reasons for the run-in period include opportunities to: 1) assess participant's ability to complete trial assessments, 2) facilitate building of a rapport between the CHE and participant, and 3) ensure CHEs have the time needed to provide participants with proper orientation to the project and assistance completing surveys and study assessments. Because this pilot project will assess feasibility, this information is essential to determine acceptability of the project protocol.

All data collection materials will be provided to participants in Spanish or English based on the participants preferred language. For participants with low literacy, the CHEs are trained to assist in completing surveys without leading responses. Demographic, clinical characteristics, mediators of behavior change within domains framed within SCT and SDT, psychosocial and quality of life outcomes, stress, and acculturation will be assessed at T1. Details regarding data collection methods for these outcomes can be found in Table 4. Measurement Tools, Data Collection Timing, and Timing of Intervention Activities ([Appendix D](#)). Baseline survey materials are found in [Appendix E](#).

The baseline data collection will include completion of an electronic (e) eConsent form via a secure HIPPA-compliant REDCap interphase and the following assessments: 1) online self-administered questionnaires

assessing demographics, medical history, clinical characteristics and self-reported height and weight; mediators of behavior change; and patient-reported psychosocial and quality of life (QOL) outcomes.

Intervention. The intervention includes six 120-minute online sessions. The participants will have access to text messages, electronic newsletters and access to interactive nutrition website. Participants will be notified of intervention start date via a phone call from the project coordinator. This will be followed by a mailed start-up study package that will include: 1) Fitbit device with detailed instructions on how to pair smartphone and sync data, 2) study activities schedule, 3) detailed instruction on how to set-up Zoom in their computers and access online sessions, and 4) study binder with written materials to be used during the online sessions. Study staff will call participants one week after receiving the start-up study package to review the materials together and answer any questions.

6.2 Intervention Overview

All participants will be assigned the goal of improving diet quality and engaging in ≥ 150 minutes per week of moderate-to-vigorous physical activity. The intervention will be based on an integrated social cognitive theory (SCT) and self-determination theory (SDT) theoretical framework to promote uptake of recommendations and target specific behavioral constructs (i.e., awareness, knowledge, self-efficacy, motivation, taste preferences, goal action planning, outcome expectations, autonomy-supportive environments).²⁵⁻²⁷

Remotely delivered online group sessions via Zoom video calls (Intervention Group). All online sessions will be held in Spanish. Resource materials and survey data will be available in both English and Spanish. The intervention will be delivered according to an intervention-specific curriculum that have been adapted to be delivered online²⁸, as we have done previously.

At least two days prior to each session CHEs will make reminder calls and send email or text messages to each study participant, depending on their preference, in order to keep attendance at sessions high and attrition low. Participants will also have the ability to contact the study coordinator via text, cell phone, office phone or email, whichever participants prefer, for any issues related to the study.

Class content: Each 120-minute session will include the following components: 1) classroom education on nutrition and PA, 2) exercise training/PA classes; 3) hands-on skills-building cooking; and 4) sharing a meal prepared by the group. **Behavioral framework:** Each activity will target specific behavioral constructs based on SCT and SDT theoretical framework: 1) classroom education (awareness, knowledge, autonomy-supportive environment); and 2) hands-on skills-building cooking and PA classes (self-efficacy, motivation, autonomy supportive environment); and 3) sharing a meal (taste preferences, goal action planning, and outcome expectations).

Timing and location: Classes will be held every other week via Zoom video calls. Participants will be provided with instructions on how to install Zoom and join Zoom video calls. Zoom video links will be sent to participants at least 24 hours prior each class via email or text, depending on participants preference. Zoom video calls will be recorded. Participants will receive a link to the recorded sessions. This will allow participants to watch it the session at a later and more convenient time.

Resources for cooking component of online sessions: All participants (n=25) will be provided with a grocery bag with the ingredients needed to participate in the hands-on cooking portion of the online sessions. Study staff will arrange the purchasing of the ingredients and will offer participants with the option to pick up the grocery bag at a convenient local grocery store or to have it delivery to participants homes either via Instacart or similar delivery service and/or by study staff, if needed. The total cost of each grocery bag is estimated at \$25 or less per session for a recipe to serve 4 or more. The ingredients provided will be based on each menu to be demonstrated by the trained Chef so participants can prepare the meals themselves at home. Once the grocery

bags are ready for pick-up or delivery, depending on participants preference, study staff will send a friendly reminder to participants and will help coordinate as needed.

Fidelity of the online group-based intervention will be assessed by an objective process evaluator, who will attend all sessions and observe and take detailed notes on the timing of the activities and delivery according to protocol. This person will not have any interaction with study participants and will not participate in data collection or study activities implementation.

6.3 Intervention Details

- **Arm A (High Dose): Online Sessions 1 to 6:** The nutrition and physical activity educator leads the classroom education part of the session (refer to table 2 for detail on topics). Participants first receive nutrition education related to increasing intakes of fruits, vegetables and whole grains; and decreasing intake of energy-dense, nutrient-poor foods (i.e., processed foods, refined grains and added sugars) via PowerPoint slides. Physical Activity. Participants then discuss being physically active in the home, review the importance of using their Fitbit device as a self-monitoring tool (technical Fitbit issues are directed to study staff after class time), and are encouraged to engage in the exercises (stretching, Zumba dance class, aerobic exercises) during the presentation tracking steps. Cooking. Participants then receive hands-on cooking classes led by the Chef and get to participate in the preparation of a meal. Finally, all participants virtually share the meal they themselves prepared at their homes with the nutrition educator and other study participants while discussing lessons learned and setting goals for the next week as prompted by the nutrition and physical activity educator.

Table 2: Online group intervention schedule and topics for high dose

Class	Classroom Education Topic	Hands-on Skills-building Cooking and Physical Activity Classes & related activities	Sharing a Meal
1	Nutrition and Activity Guidelines, Increasing Fruits and Vegetables; Introduction to aerobic exercise, using the Fitbit	Cooking : Intro to a Healthy Kitchen Physical Activity : Intro to Aerobic Exercise + Using the Fitbit to Track Exercise	
2	Reading Labels, Reducing Sugar and Finding Hidden Sugar; How to plan for Success	Cooking : Using Whole Ingredients and No Added Sugars Physical Activity : Planning exercise	
3	Healthy Fats & Proteins; Using the environment as your gym	Cooking : Cooking with Healthy Fats, Plant and Animal Protein Physical Activity : Outdoor physical activity	
4	Grocery Shopping; Learning When and How to Properly Stretch with Stretching Activity at End of Session	Cooking : Adapting Flavor to Preference Physical Activity : Optimal Stretching	Share meal, discuss barriers and facilitators, goal setting activity
5	Carbohydrates, serving sizes, meal preparation and planning; ASCM New Guidelines, Tips and Tricks for exercising at home, injury prevention	Cooking : Healthy Carbohydrates Choices Physical Activity : Exercise for Injury Prevention	
6	Eating, Moving and Cooking for a Healthy Future; How to maintain physical activity as a lifestyle and community and online resources.	Cooking : Physical Activity : Community and Online Resources	

6.4 eHealth Communication

Electronic (e) Health (eHealth) communication materials are found in [Appendix G](#), including sample text messages and sample newsletters content. Seattle-based study staff oversee the eHealth component.

Participants in both arms will receive 12 weeks of motivational text messages 2-3 times per week and link to access the nutrition cookforyourlife.org website. eHealth communication messaging will focus on increasing fruits/vegetables intake and reducing intakes of energy dense and processed foods and increasing PA using constructs of the SCT and SDT. Participants will be prompted to respond on average to one of the weekly text messages (i.e., Think about yesterday. Did you eat 5 or more servings of fruits and vegetables?) Study staff will respond to participants as needed if any specific questions arise. The eHealth text topics and schedule are presented in [Table 3](#).

Table 3: eHealth text topics and schedule (16 texts per month)

Target behavioral construct	Nutrition texts (50%)	Physical activity texts (50%)
Skill-building	2/month	2/month
Goal-setting	2/month	2/month
Motivation	1/month	1/month
Knowledge	1/month	1/month

6.5 Activity Monitoring

All participants will use both devices: participants will wear Fitbit Inspire on the wrist. Participants do not have to wear Fitbit during sleep. The wearing time of each device is outlined below.

Device	Duration
Fitbit Inspire	Baseline to 3 months follow-up data collection, on wrist

Participants will be trained to monitor their step count on smartphone and Fitbit. Participants should perform activity monitoring by checking the step counts by looking at the screen of their Fitbit Inspire and the Apple Health/Google Fit app. The purpose is to make participants aware of their activity level throughout the day. Participants are not required to change their usual activities according to the step count but are encouraged to progressively achieve ≥ 150 minutes per week of MVPA as displayed by the Fitbit physical activity tracker. Participants will receive monthly check-in calls, texts and/or emails to inquire about device usage and troubleshooting.

6.6 Retention

To improve retention CHEs will conduct a brief monthly follow-up telephone calls during month 2 of the 3 months intervention to all study participants. Staff will thank participants for their continued participation in the study, and will ask questions about (1) COVID-19 incidence, exposure, testing, related-symptoms and whether they have felt isolated during the pandemic, (2) Fitbit use, and (3) will help troubleshoot any issues associated with Fitbit devices. In month 3, participants will be encouraged to complete data assessments, as needed and even if participants do not completely adhere to the intervention.

In the event that a study participant's phone is disconnected, or if a participant stops responding to our calls or text messages after 4-6 attempts, study staff will mail a letter to study participants' home address and will send an email message indicating that we have had trouble reaching them. We will encourage study participants to get in touch with us and to provide us with a new phone number so that they can be contacted to answer study questions by phone, and if able, complete the in-person clinic visits.

6.7 Follow-up 3 Months Data Collection.

At 3 months, participants will repeat baseline measures (see Table 1) and complete a short exit interview to assess intervention acceptability.

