In October 2021, investigation into the reason for slow recruitment (n=22 to date) revealed a high burden of data collection for potential participants. In addition, preliminary analyses of data currently being collected by [name] in a similar intervention among a predominantly non-Hispanic white population of urban breast cancer survivors suggested a minimal effect of the low dose arm. As such, Drs. [name] and [name] decided to adapt the study as follows: change the design to be a single-arm feasibility study in which all participants receive the full “high-dose” intervention, decrease the target recruitment goal, and decrease participant burden by removing intensive data collection methods. These modifications will yield valuable information to determine how best to proceed with future diet and physical activity behavioral interventions in this rural population.

Overview of Study Design. The proposed pilot study will recruit 25 Latinos who are residents of the rural Lower Yakima Valley (LYV) with one or more of the following diagnoses based upon self-report: hypertension, diabetes, cardiovascular disease, obesity, or a history of cancer. Recruitment, retention, and data collection procedures will be carried out by Community Health Educator (CHE) study staff. Eligible participants will undergo online baseline assessments over a period of 1-2 weeks. Interested and eligible participants will be sent an online informed consent, HIPPA and medical records release form and baseline questionnaires to complete.

Following the completion of baseline data collection, participants will receive the intervention. All participants will receive a Fitbit device to self-monitor their PA. The intervention will include 6 biweekly 2-hour Zoom-based nutrition, culinary, and physical activity sessions. The sessions will be led by a local chef consultant and CHE, both trained by the study team. Participants will receive eHealth communication meant to motivate healthy diet and improved PA via educational and motivating text messages and using resources available as part of the study-related website over a 3-month period. Following completion of the 3-month intervention period, repeated baseline at-home assessments will take place and an exit intervention completed. The exit interview will include questions regarding acceptability and accessibility of the intervention for participants.

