7.1.2 Retention calls and data collection

- 1) During monthly retention call participants will be asked about use of and technical issues with their study Fitbits. These data will be recorded to understand Fitbit usage patterns.
- 2) During monthly retention call, participants will be asked about COVID-19 symptoms, testing and isolation. These data will be used to examine the effects of the COVID-19 pandemic on intervention adherence patterns.

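### No participant contact described in the protocol body is said to ask about the harms named in Section 2.3, so mild and moderate adverse events will tend to be undercounted

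*Combined protocol and SAP*

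**What the plan says.** Section 2.3 calls research-related injury highly unlikely but names what may happen: injuries while cooking, dancing or exercising, soreness and joint pain from more activity, and gas and bloating from more fiber. Section 10.1 sends any adverse event to a summary form (Appendix I). The scale in Section 10.2 starts at discomfort that does not interrupt daily life (grade 1) and moves to discomfort that changes it (grade 2). The same section has the PI review all events cumulatively and puts their number in the annual IRB report.

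The contacts through which an event could be learned are described as follows.

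- Start-up call (Section 6.1): "Study staff will call participants one week after receiving the start-up study package to review the materials together and answer any questions".
- Device check-ins (Section 6.5): "Participants will receive monthly check-in calls, texts and/or emails to inquire about device usage and troubleshooting".
- Retention call in month 2 (Section 6.6): staff "will ask questions about (1) COVID-19 incidence, exposure, testing, related-symptoms and whether they have felt isolated during the pandemic, (2) Fitbit use", and they help with device problems. Section 7.1.2 agrees: "During monthly retention call participants will be asked about use of and technical issues with their study Fitbits". It adds the COVID-19 questions, whose stated use is to examine adherence.
- 3-month follow-up (Section 6.7): "participants will repeat baseline measures (see Table 1) and complete a short exit interview to assess intervention acceptability".
- Exit interview (Section 1.0): "The exit interview will include questions regarding acceptability and accessibility of the intervention for participants".

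Participants can also raise matters themselves. Section 6.2 says "Participants will also have the ability to contact the study coordinator via text, cell phone, office phone or email".

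**The concern.** Sections 10 and 11 set out what happens once staff know of an event: record it, grade it, report it, review it. They do not say who asks participants about harms, when, or in what words. A participant with a sore knee or bloating has no described occasion on which the subject is raised.

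At stake is the meaning of the adverse event count. Without a standard question, a low count cannot be told apart from events that nobody thought to mention, and those events cannot be recovered at analysis. The count goes to the PI's review and the IRB. The pilot is also meant to guide later trials of this program in a population now widened to people with hypertension, diabetes, cardiovascular disease or obesity (Section 1.0). Delivery is fully remote, so staff see little of the activity that they encourage.

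**Working it through.** The protocol states no adverse event rate, so there is no figure to reproduce. The check sets the commitment to count beside the described content of each contact.

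**Step 1. What is to be counted.** Any adverse event (10.1), from grade 1 discomfort upward (10.2). The harms in 2.3 would mostly fall in grades 1 and 2.

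**Step 2. What each contact is described as asking.**

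| Contact | Section | Described content |
|---|---|---|
| Start-up call | 6.1 | materials, participant's questions |
| Session reminders | 6.2 | attendance |
| Sessions | 6.3, Table 2 | teaching, exercise, cooking; staff-led talk on lessons, goals, barriers and facilitators |
| Prompted texts | 6.4 | diet and activity behavior |
| Device check-ins | 6.5 | Fitbit use and faults |
| Month-2 call | 6.6, 7.1.2 | COVID-19, Fitbit |
| 3-month measures | Table 1, 7.1.1 | weight, physical activity questionnaire, knowledge and preferences, self-efficacy, motivation, stress, quality of life |
| Exit interview | 1.0, 6.7, 13.2 | acceptability and accessibility |

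None is described as asking about the 2.3 harms. Comorbid conditions and medical history are collected at baseline only (13.3), so they do not fill the gap.

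**Step 3. What routes remain.** Participant-initiated contact (6.2), session discussion (6.3), replies to texts (12.0) and reasons for withdrawal (10.2). Staff told of an event are trained to report it at once (11.0). Each route depends on the participant bringing the event up or on staff noticing it.

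**Step 4. Direction.** Let p be the true share of participants with a mild or moderate event and d the share of those that reach staff. With N = 25:

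- expected number affected = 25 × p
- expected number recorded = 25 × p × d

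Since d cannot exceed 1, the recorded number can only be equal or lower on average. The documents give neither p nor d. Purely as assumed values, p from 20% to 40% gives 5 to 10 participants affected. With d from 25% to 75%, between 25 × 0.20 × 0.25 = 1.25 and 25 × 0.40 × 0.75 = 7.5 would be recorded. This range shows how the formula behaves and is not an estimate for this trial.

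**Step 5. How a zero count would read.** If none of 25 participants had a recorded event, the exact 95% upper limit is:

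- two-sided: 1 − 0.025^(1/25) = 13.7%
- one-sided: 1 − 0.05^(1/25) = 11.3%

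Both limits apply to the true share only if d = 1, which volunteered reporting cannot establish. The protocol plans no such estimate; the figures show only what a reader might wrongly take from a clean record.

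**The case against.** The strongest reply is that the instruments themselves are not visible. Appendix D (measurement tools and timing), Appendix E (survey materials) and Appendix I (adverse event form) are cited but not in the available document, and the exit interview questions are not reproduced. Table 1 names instruments, not items, and the quality-of-life questionnaire may touch on symptoms. This stands as a limit: a reader might infer that no instrument asks about harms, and the documents do not support that. They support only that none is described as doing so.

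Second, the sessions are a planned, staff-led occasion on which soreness or injury could come up as a barrier. The fidelity observer cannot take that role, since "This person will not have any interaction with study participants and will not participate in data collection or study activities implementation", but this says nothing about the educator, chef and community health educators who run or assist the sessions. An event between sessions can be mentioned at the next one. This stands too: the route is real, though not aimed at harms and not asked of everyone in the same way.

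Third, proportionality. Section 10.1 calls the study low risk, adverse events are not an endpoint at any level, and the grade 1 wording is compatible with passive capture. Related serious events go to the IRB within 7 days of the investigator's being notified, and terminations due to an adverse event reach the PIs within 24 hours. This lowers the weight of the point. It does not remove the protocol's own undertaking to record and count mild events.

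Fourth, timing. By October 2021, 22 participants had been recruited toward a target of 25, and funding runs to December 31, 2021. Some may already be past month 2, so the gain may be partial.

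**Conclusion.** The point holds as a gap in ascertainment. As the protocol body is written, mild and moderate events are captured through what participants volunteer, including in session discussion, and counts will tend to be low. Only the direction is supported; the size cannot be derived. The conclusion assumes that staff follow the described contact content and that no unseen appendix contains a standard harms question.

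Two stronger readings should be resisted. A reader might infer that the trial has no safety capture, or that serious events will be missed. Sections 10 and 11 provide recording, grading, staff training and prompt reporting, and nothing in the documents shows that serious events would go unnoticed. A reader might also infer that the feasibility results are compromised. Accrual, adherence, retention and acceptability do not depend on how adverse events are elicited.

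This is a cheap improvement to safety data collection, worth making but not a flaw in the main purpose of the study.

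**What to change.** In Sections 6.6 and 7.1.2 (month-2 call) and Section 6.7 (3-month assessment), add one open question: any injury, pain, digestive or other new health problem since the last contact, and whether it limited activity or needed care. Record answers on the existing Adverse Event Summary Form with the Section 10.2 grade. In the descriptive summary, report the number of participants with at least one event by worst grade, and how many were asked at each contact. If Appendix D, E or I already contains such a question at a set contact, cite it in Section 10.1 instead.

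The cost is at most 25 × 2 = 50 askings at contacts that already take place, one amendment, and question wording in English and Spanish. The downsides are a little more burden in a version written to reduce it, more mild events to grade, and mixed ascertainment if some participants have already passed month 2. Reporting the number asked makes that last point visible.
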